6. STUDY DESIGN

This project consists of three randomised multiple baseline design (MBD) single case experimental design studies, with an A₁B₁A₂ structure (Appendix A).

Each study will have four participants. After completing a baseline assessment, each will be randomised to a different length of baseline (phase A₁) duration (either 1, 2, 3 or 4 weeks). During A₁, participants will rate the target maintenance mechanism (factor) and their level of dissociation daily (see Section 9.6, *Assessments*).

The treatment window (phase B₁) for each participant in all studies will be five weeks. In this time, participants will have four 1:1 one-hour long psychological therapy sessions with a qualified clinical psychologist who will deliver the study intervention (see Section 10, *Study Interventions*). Between-session tasks will be set as part of this intervention, to be completed by the participant alone, or with telephone or additional in-person support from the research team. Participants will continue to rate the maintenance mechanism factor and their dissociation every other day. At the end of the intervention window (phase B₁), participants will repeat the baseline assessment measures in a ‘post-intervention’ assessment.

The follow-up phase – phase A₂ – will last for one month following the closure of the intervention window (phase B₁). In this phase, participants will continue to make ratings of the maintenance mechanism factor and their dissociation every other day. At the end of phase A₂, participants will complete the baseline assessment measures again in a ‘follow-up’ assessment, and will be offered the chance to provide unstructured qualitative feedback about the research processes and intervention.

This project will be registered with ClinicalTrials.gov.

7. PARTICIPANT IDENTIFICATION

7.1. Participants

The target population is people attending NHS mental health services for an Axis I mental health difficulty who are also experiencing high levels of dissociation. Evidence indicates that such experiences are common across mental health diagnoses¹⁴.

7.2. Inclusion Criteria

- Aged between 16 years to 80 years;
- Outpatient of mental health services (at the time of referral to the study);
- Experiencing significant levels of ‘felt sense of anomaly’-type dissociation (defined as a score within the ‘moderate severe’ or ‘severe’ range on the CEFSA-14 (i.e., score of 39 or above); [name] *et al.*, *in prep.*);
- Want help to improve their dissociative experiences;
- Willing and able to give consent for participation in the study;
- Available to undertake the baseline assessment in the indicated week;
- Available to undertake the therapy sessions within the indicated therapy ‘window’.

7.3. Exclusion Criteria

The participant may not enter the study if ANY of the following apply:

[figure not shown]
- Diagnosis of an Axis II (“personality”) disorder;
- Primary diagnosis of alcohol/substance dependency, organic syndrome, or learning disability;
- Presence of risk issues that would be a clinical priority above managing dissociative symptoms (e.g., moderate to severe self-harm; active suicidal behaviour; etc.);
- Current engagement in any other individual psychological therapy (or psychological therapy due to begin within the participation window for this study).
- A participant may also not enter the study if there is another factor (i.e., with higher clinical priority), which, in the judgement of the investigator, would preclude the participant from providing informed consent or from safely engaging with the study procedures. Reason for exclusion will be recorded in line with CONSORT 2010 Statement²⁹.

8. STUDY PROCEDURES

The study flow chart is shown in Appendix A, and a schedule of procedures is summarised in Appendix B.

After screening and consent, participants will have seven study visits: three assessments, and four therapy sessions.

All participants will complete three assessment visits with a research assistant. The first is at baseline (0 weeks). The second, ‘post-intervention’ assessment, will occur as soon as practicable after the five-week intervention window has closed (i.e., within the next working week). The exact timescale for the second assessment will therefore vary, since each participant will be randomly allocated to wait either one, two, three, or four weeks between the baseline (0 weeks) assessment and the start of the intervention (see diagram below). All ‘follow-up’ assessments will take place one-month after the participant’s post-intervention assessment. Additionally, all participants will complete a brief (two-item) survey via telephone, text message, or online survey (via Qualtrics) daily throughout the pre-intervention phase, and every other day during the intervention and follow-up phases; see Section 9.6 ‘Assessments’.

All participants will receive the intervention for that study (i.e., targeting cognitive appraisals [study 1]; perseverative thinking [study 2]; or affect intolerance [study 3]). Four 1:1 therapy sessions will take place within the five-week intervention window. This allows some flexibility for therapist and participant in the case of absence, illness, or other difficulty scheduling appointments. More detail is given in Section 10, ‘*Study Interventions*’.

We will inform participants’ relevant clinical team that they are taking part in the study (e.g., via the clinical notes system, or feedback to the referring clinician).

8.1. Recruitment

The recruitment target is 12 participants (four participants in three studies). Recruitment will be conducted in two local NHS mental health trusts: Birmingham Women’s and Children’s NHS Foundation Trust, and Birmingham and Solihull NHS Foundation Trust. Participants will be recruited from the NHS services accessible to help-seeking people aged 16 and over. The services include specialist early intervention in psychosis services (EIP: ages over 14 years), and adult mental health teams (AMHTs), as well as Psychological Services. Support for the project has been established with the relevant clinical leads; notably within the early intervention in psychosis service (Forward Thinking Birmingham), and with the Lead for Psychological Therapies.

The principal method of recruitment will be from routine clinical services. The clinical team or clinical research network (CRN) staff will identify potential referrals from the team caseload and provide potential participants with the participant information sheet (PIS). Additionally, the lead researcher for this study works within clinical services one day a week, and may therefore also identify referrals and approach patients as part of their clinical role. If participants confirm they are happy to be contacted by the research team their contact information will be passed on the research team for this purpose. The research team will make a note of the verbal consent in their contact records. If participants do not want their contact details passed on to researchers at this time, they may retain the PIS and contact the researchers themselves at a later stage.

In a previous study with similar recruitment methods, the Lived Experience Advisory Panel (LEAP) for that trial emphasised the importance of patients also self-initiating referral to the study, in order to minimise the chances that particular patients are overlooked by clinical teams or the clinician was not present at a referral meeting. Therefore, we will also advertise the study (including via social media, online, posters present in NHS buildings, and other relevant sites). Hence, patients will be able to self-refer to take part in the study. However, in all instances we will also seek to confirm that a member of their clinical team gives approval for a patient to enter the study.

8.2. Screening and Eligibility Assessment

The eligibility assessment will be conducted by a research assistant under the supervision of a qualified clinical psychologist. The screening will take place at either an NHS clinical base, University clinical research site, or the patient’s home, depending on their preference.

The eligibility assessment will include confirmation of the key clinical problem and availability for participation including:

- Self-report questionnaire assessing dissociation (ČEFSA-14; [name] et al., *in prep.* – based on the original ČEFSA²¹);
- Confirming that the patient meets inclusion and exclusion criteria – particularly clinical assessment / confirmation of the clinical team’s assessment that there are no imminent risk

issues that would take clinical priority for treatment (see section 8.3 ‘*Exclusion Criteria*’);

- Checking that the patient is available to participate according to the anticipated schedule of the study: i.e., that they would be able to undertake the baseline in the designated week, would be willing to commit to four sessions of therapy, are not anticipating extended absences during the weeks in which the intervention window may fall, and will not be commencing any psychological therapies within the study participation period.

The above discussion and completion of the ČEFSA questionnaire will take place under informal verbal consent of the patient and implied consent through completion of the questionnaires on the understanding that the purpose of these activities are to determine the applicability of the research to the patient, thus minimising the risk of them beginning a burdensome research assessment under formal written consent only to discover that the study is irrelevant to them. The patient will be made aware that any discussion notes or questionnaire forms completed during the eligibility assessment will be securely destroyed once (in)eligibility has been determined and their contact details will be deleted at the end of the study.

8.3. Informed Consent

Written informed consent will be obtained by either the research worker (who will be sufficiently trained for this purpose) or a qualified clinical psychologist from the research team. This will be after the clinical team approval to approach the patient, provision of the participant information sheet to the patients, opportunities to ask questions and at least 24 hours to decide.

Written or electronic versions of the Participant Information Sheet (PIS) and Informed Consent Form (ICF) will be presented to the participants detailing no less than: the exact nature of the study; what it will involve for the participant; the implications and constraints of the protocol; the known side effects and any risks involved in taking part. It will be clearly stated that the participant is free to withdraw from the study at any time for any reason without prejudice to future care, and with no obligation to give the reason for withdrawal.

The participant will be allowed as much time as wished to consider the information, and the opportunity to question the Investigator, or other independent parties to decide whether they will participate in the study. Written informed consent will then be obtained by means of participant dated signature and dated signature of the person who presented and obtained the ICF. If completed electronically, typed signatures will suffice. Copies of the consent form will be retained in the researcher site file, provided to the participant, and uploaded to the participants’ electronic medical records.

Young people aged 16-18 years can be considered competent to consent to research and therefore, no parental consent to participate in the project will be sought. A qualified clinical psychologist trained in assessing capacity will assess the potential participant’s competence to consent to research if they are aged 16 or 17 years. If aged 18 years or above, capacity to consent will be assessed by a GCP-trained research assistant, with further assessment by the clinical psychologist in cases where capacity is unclear.

8.4. Randomisation

Randomisation will be carried out by a researcher outside of the study team. They will randomly allocate a baseline phase duration (one, two, three, or four weeks³⁰) to a letter (A, B, C or D). This will be repeated for each of the three studies. Allocations will be recorded via the use of sealed envelopes, which will be stored securely by the CI. At each baseline assessment appointment, after the measures have been completed, the research assistant will select envelope A for the first participant, B for the second, and so on, and open the envelope to reveal to the participant how long their randomly-allocated baseline phase will be. This will then be recorded in the baseline CRF and communicated to the therapist.

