8.6. Assessments

All participants will undertake the baseline assessment in the same week, following a concurrent randomised multiple-baseline study design. Participants will undertake three assessment visits with the research assistant (these are referred to in SCED terminology as ‘standard’ assessments), and frequent ratings of the two primary constructs between assessments, throughout the course of the study (these are referred to as ‘target’ assessments)³¹. All assessments will use a study ID in place of identifying information.

9.6.1 ‘Standard’ Assessments

The baseline, post-intervention, and follow-up assessments will each last approximately 50 minutes. The assessment will be conducted at an NHS or University of Birmingham building, or the participant’s home, based on participant preference. The assessment will be conducted on an individual basis, with only the participant and researcher present. Assessments can be conducted remotely (for example using telephone, online, or postal versions) if necessary. Online assessments may be in the form of either: the participant annotating an electronic (Word document) version of the measures; the RA annotating a hardcopy or electronic copy of the measures whilst on a call with the participant; or via Qualtrics. Self-addressed stamped envelopes will be provided for participants returning measures by post, in the case that it is not practicable for the RA to collect these in person to ensure safe receipt.

All assessments in the study are self-report measures; except for the recording of the participant’s clinical diagnosis and current prescribed medication, which will be extracted from their clinical records at each assessment point. Permission to access clinical records for this purpose will be obtained during the informed consent process.

The self-report outcomes collected at all three standard assessments are:

1. ‘Felt sense of anomaly’ (FSA)-type dissociative symptoms:

- [name] Felt Sense of Anomaly scale – revised (ČEFSA-14; [name] et al., *in prep.* – based on the original ČEFSA²¹)
- Visual analogue scale (VAS) rating 0-100 for FSA-dissociation.

2. Possible mechanisms of FSA-type dissociation:

- Cognitive Appraisals of Dissociation in Psychosis scale (CAD-P²);
- Perseverative Thinking Questionnaire (PTQ⁵);
- Affect Intolerance Scale (AIS¹);
- Online Alexithymia Scale (amended) (OAS⁴);
- General Self Efficacy scale (GSE³);
- Responses to Dissociation scale (RTD⁴).

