11.2. Sample Size Determination

The aim of SCED studies is to use repeated phases with and without the application of the experimental intervention to demonstrate that it is the intervention that is causing the observed effect. In essence, this allows the same participant to contribute both control and intervention data, increasing information about probable cause and effect in contexts where it may not be feasible to run a fully powered randomised controlled trial³¹. General convention suggests that demonstrating changes in the outcome measure after introducing or withdrawing the intervention must be done a minimum of four

times to imply a functional relationship between intervention and effect⁴⁰. Typically, this can be achieved by repeatedly introducing and withdrawing an intervention with the same participant. However, this method is less valid in clinical psychology, where carry-over effects are expected from the intervention, and repeating the intervention may not be practicable. Thus, the multiple-baseline design (MBD) across individuals allows the requisite number of transitions (from intervention to ‘no intervention’ and vice versa) to be achieved, whilst each participant only undergoes the treatment once. Randomising the length of the baseline phase for each participant means that any observed effect cannot be better understood as a function of time elapsed since the baseline assessment or other research procedure. The minimum number of participants required for an MBD study is two, although three or more is typical⁴². Thus, this project will use a sample size of four participants per study, to mitigate against any potential drop out or high levels of missing data.

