22. APPENDIX A: STUDY FLOW CHART

23. APPENDIX B: SCHEDULE OF PROCEDURES

Procedures	Screening	Baseline (0 weeks) assessment	Baseline phase (A ₁) (1, 2, 3 or 4 weeks)	Intervention window (B ₁) (5 weeks)	Post-therapy Assessment	Follow-up phase (A ₂) (1 month)	Follow-up Assessment
Study procedures							
Eligibility assessment	X						
Informed consent		X					
Randomisation		X					
Adverse event monitoring	X	X	X	X	X	X	X
Data collection							
Demographics		X					
Diagnosis and medication (from clinical records)		X			X		X
Measure of FSA-dissociation (CEFSA-14)		X			X		X
Measures of feasible maintenance mechanisms (CAD-P; PTQ; AIS; OAS; GSE; RTD)		X			X		X
Self-harm		X			X		X
VAS scales (dissociation; study-specific mechanism)		X	X*	X**	X	X**	X
Qualitative feedback regarding therapy and study							X
Interventions							
NHS treatment as usual	X	X	X	X	X	X	X
Study intervention (4 sessions)				X			

Key: * = daily; ** = every other day

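### Opening the four envelopes one at a time from a known set of waits weakens concealment for the later participants in each study

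*Combined protocol and SAP*

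**What the plan says.** - **The set of waits.** Section 6 says of the four participants in a study that "each will be randomised to a different length of baseline". Section 8.4 describes how a researcher outside the study team prepares this: "They will randomly allocate a baseline phase duration (one, two, three, or four weeks³⁰) to a letter (A, B, C or D"). This is repeated for each study, and the results are kept in sealed envelopes held by the chief investigator.
- **The opening.** Section 8.4 has this happen at the person's own baseline visit, once that person's questionnaires are done: "the research assistant will select envelope A for the first participant, B for the second, and so on, and open the envelope". The participant is told at once, the wait is entered in the CRF, and the therapist is informed.
- **Timing of visits.** Section 8.6: "All participants will undertake the baseline assessment in the same week, following a concurrent randomised multiple-baseline study design". Section 8 has participants "randomly allocated to wait either one, two, three, or four weeks between the baseline (0 weeks) assessment and the start of the intervention", so each wait runs from that person's own visit.
- **Timing of consent.** Appendix B marks "Informed consent" only in the baseline assessment column, the same column as randomisation. The opening of Section 8 instead puts screening and consent ahead of the seven study visits.
- **Staff.** A research assistant does the eligibility assessment (Section 8.2) and the assessment visits (Section 8). A research worker or a team psychologist takes consent (Section 8.3). There is no blinding (Section 8.5).
- **Purpose.** Section 11.2: "Randomising the length of the baseline phase for each participant means that any observed effect cannot be better understood as a function of time". The time meant there is time since the baseline visit or another study procedure.

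Nothing in the document ties letters to named study IDs in advance, or holds the envelopes until all four participants have consented.

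**The concern.** An outside randomiser and sealed envelopes are there so that nobody who enrols participants can know the next allocation. With only four distinct waits, each used once, every opening reveals something about those still sealed. By the third visit two waits remain; by the fourth there is one.

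The staff who screen, may take consent and run the baseline visit overlap with the person who opens the envelopes. Availability for the therapy window is an inclusion criterion (Section 7.2). If the only wait left suits the next person badly, or seems unwise for that person, someone could put off the visit, decline to proceed, or bring in another candidate. The wait would then depend partly on who the participant is. Section 11.2 relies on that not happening, and with four people per study one substitution affects a quarter of the cohort.

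The exposure is greatest if consent is taken at the baseline visit, as Appendix B has it, because the remaining waits are then known before later participants have agreed to take part.

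**Working it through.** **The plan's own figure.** 3 studies × 4 participants = 12, as the synopsis states: one participant per wait per study. The document gives no figure for predictability or for calendar spacing.

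**Predictability.** Inputs: four known waits, used once each (Sections 6 and 8.4), opened in sequence. Before the k-th envelope is opened, 4 − (k − 1) waits remain, each equally likely, so the chance of naming the next one is 1/(4 − (k − 1)).

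| Participant | Waits remaining | Chance of a correct guess |
|---|---|---|
| 1 | 4 | 1/4 |
| 2 | 3 | 1/3 |
| 3 | 2 | 1/2 |
| 4 | 1 | 1 |

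Expected correct guesses = 3/12 + 4/12 + 6/12 + 12/12 = 25/12 = 2.08 of 4 (52%). With all four opened together: 4 × 1/4 = 1.00 of 4 (25%).

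**Can visit order steer the allocation?** The waits are randomly attached to letters and sealed, so whoever is seen next receives a uniform draw from those left. As a check, 2,000 adaptive rules were tried. Each chose the next participant from everything revealed so far, and each was run against all 4! = 24 orderings of the waits. Every rule produced each of the 24 allocations exactly once. With a fixed set of four people, reordering leaves the allocation fully random. What remains is a change in who the four people are, or whether a later one goes ahead.

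**Consent timing.**
- Appendix B reading: participants 2 to 4 may consent after one, two and three waits have been revealed.
- Section 8 reading: all four could have consented before any envelope is opened. The remaining waits are then known only before the later participants' visits and baseline measures.

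**Calendar spacing (secondary).** Let d be the weekday of a person's baseline, Monday = 0 to Friday = 4. Weekdays are an assumption; Section 8.6 says only the same week. Adjacent therapy windows open 7 + (d of the longer wait − d of the shorter wait) days apart: 7 − 4 = 3 at the least, 7 + 4 = 11 at the most, and exactly 7 if the visits share a day.

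**Would a common start date help?** If all waits ran from one date and ratings began at each person's own visit, calendar gaps would be 7, 7, 7. The A1 length would become 7 × wait + (common date − own visit date). Adjacent A1 lengths would then differ by 7 − (difference in d), again 3 to 11 days. Over all 5^4 = 625 weekday combinations, taken as equally likely, some adjacent difference is 4 days or less in 216 (34.6%), and all three equal 7 in 5 (0.8%). The present rule gives the same counts for calendar gaps. The unevenness is moved, not removed.

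**The case against.** The strongest reply is that guessing is not steering. The figure of 2.08 measures what staff can predict, and the check above shows that they cannot use visit order to send a chosen wait to a chosen person. When the last wait is certain, only one participant is left to receive it. That stands: a reader might infer that rescheduling decides who gets which wait, and the design does not allow it.

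Three further points have force.
- Section 8.2 screens availability across the weeks in which the window may fall, and everyone in a study receives the same therapy. There is no preferred arm, so the motive to select is weaker than in a two-arm trial.
- A reader of Appendix B alone might conclude that later waits are known before consent. The opening of Section 8 says otherwise, so this is a conflict to settle, not an established fact.
- A reader might also infer that the therapy windows will open 3 to 11 days apart instead of 7. The document promises no calendar spacing and gives no visit weekdays; 3 to 11 is an outer range under a Monday–Friday assumption. Each person's wait from their own baseline is exact, so the aim in Section 11.2 concerning time since baseline is untouched. Uneven spacing loosens only the control for events shared in calendar time.

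The reply does not answer selective consent, deferral or replacement. Screening for availability narrows that route, but no provision closes it once remaining waits are known.

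**Conclusion.** The point holds in a limited form. Sequential opening from a known set gives the research assistant the fourth wait with certainty and the third to within two, for 2.08 expected correct guesses of 4 against 1.00 under concealment. This rests on the waits being used once each and the envelopes being opened as Section 8.4 describes. It assumes nothing about how staff would behave, and the document gives no means of estimating how often knowledge of a wait would change an enrolment decision.

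The consequence is weaker concealment, not a demonstrated bias. It is more serious if Appendix B governs consent than if Section 8 does. Analysis is descriptive with no significance testing (Sections 11.1 and 11.5), so no error rate is at stake. What is at stake is how far the causal judgement can lean on random wait lengths.

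Calendar spacing should be described only as able to range from 3 to 11 days if baselines fall on different weekdays (Monday–Friday assumed), and exactly 7 if they share a day. It does not justify a common start date.

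**What to change.** **Section 8.4.** Assign letters A–D to study IDs before the baseline week. Obtain all four consents before any envelope is opened. Open all four together after the fourth participant has completed the baseline measures. Every wait then has a 1/4 chance of being guessed before opening.

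**Section 8 and Appendix B.** Reconcile the two statements on when consent is taken, consistently with the rule above.

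**Leave unchanged.** Keep each wait counted from the person's own baseline visit, as Section 8 states. Do not add a common day 0.

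**Cost.** The change is to wording and to the order of steps. With Monday–Friday visits, the first participant learns the wait up to 4 days later; if it is the one-week wait, 7 − 4 = 3 days' notice remain. A late fourth visit delays the opening for everyone. Section 8.4 should therefore say what happens if that visit slips, since a slip to 7 days or more after the first visit would overrun a one-week wait.
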